##### **Confidentiality Statement**

The number and percent of values BLOQ or above ULOQ will be presented in each summary table.

For CYP2A6 activity, any values BLOQ or above the ULOQ in the denominator will not be imputed and the derived variable will be presented as "Not Calculated" in descriptive summaries.

Questionnaire data total scores and domain or subscale scores may use a certain degree of imputation (by averaging across individual item scores) as detailed in Section 7.3 "Questionnaires". For assessment of cough, if no cough was reported at a given visit then the VAS score is imputed with zero.

If an actual sampling time or  $T_0$  fix or  $T_0$  ad lib is missing from the dataset, the corresponding nominal sampling time will be used instead.

If time of discharge is missing, then it will be imputed by 8pm of the day the subject was discharged.

Partial dates will not be imputed, but assumptions will be made as follows to assign to either medical history or concomitant diseases (Table 17), to assign to either product-emergent or non-product emergent adverse events (Table 18) and to assign to either prior or concomitant medications (Table 19):

**Table 17 Partial Dates for Medical History or Concomitant Diseases**

Date information	Assign as
Missing stop date	Concomitant disease
Partial date, e.g. --May2012, or ----2011. If month/year is the same as, or later than the month and/or year of Screening.	Concomitant disease
Partial date, e.g. --May2012, or ----2011. If month and/or year is earlier than the month and/or year of Screening.	Medical history

**Table 18 Partial Dates for Adverse Events**

Date information	Assign as
Partial date, e.g. --May2012, or ----2011. If month/year is the same as, or later than the month and/or year of Visit 2	Product-emergent
Partial date, e.g. --May2012, or ----2011. If month and/or year is earlier than the month and/or year of Visit 2.	Not product-emergent

**Confidentiality Statement**

**Table 19 Partial Dates for Prior and Concomitant Medications**

Date information	Assign as
Missing stop date	Concomitant
Partial date, e.g., --May2012, or ----2011. If month/year is the same as, or later than the month and/or year of Screening.	Concomitant
Partial date, e.g., --May2012, or ----2011. If month and/or year is earlier than the month and/or year of Screening.	Prior

### **12.1.5.1 Insufficient Data for Analysis/Presentation**

If there are no values/event at the general value then the break out should not be presented. For example if the number of related AEs is zero then no presentation by severity of related events at the single level will be produced.

Some of the TFLs may not have sufficient numbers of subjects or data for presentation. If this occurs, the blank TFL shell will be presented with a message printed in the table, such as, "No serious adverse events occurred for this study."

Summaries will be limited when there are less than 4 assessments available for analysis, and only the number and percent of subjects available (by strata if applicable) and non-parametric summaries (min, max, median, quartiles) if applicable, will be presented.

### **12.1.6 Handling of Unplanned Data**

Unscheduled post-product use assessments will be excluded from the summary statistics and only included in listings. Unscheduled assessments will be labelled as unscheduled in the listings and mapped to the study day using the date of the study day until midnight.

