8 ADVERSE EVENTS

8.1 Definitions

8.1.1 Adverse Events

An adverse event (AE) is defined as any unfavourable and unintended sign (including an abnormal laboratory finding), symptom, or disease temporally associated with the use of a product or a study procedure, whether or not related to the product or the study procedure. Careful Investigator's medical judgment is required to establish whether a clinical finding (including an abnormal laboratory result) is a true AE or just a manifestation of a preexisting health – related condition.

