8.4 Reporting of Other Events Critical to Safety Evaluations

8.4.1 Abnormal Results of Laboratory Tests

Any clinical safety laboratory test result that is outside of the normal reference range will be reviewed by the Investigator and assessed for clinical significance according to its severity. The severity of abnormal laboratory test result must be assessed using CTCAE version 4.03 grading scales (Appendix C). Any clinical safety laboratory test result that is outside of the normal reference range will be reviewed by the Investigator and assessed for clinical significance according to its severity. Whenever that grading scheme is not available for the laboratory result of concern, the Investigator should assess the severity and the clinical significance of that result using his/her medical judgment.

Subjects with clinically significant abnormal laboratory values at Screening will not be enrolled. Abnormal laboratory test results detected at the Screening Visit whose CTCAE grades are 2 or higher or still are CTCAE grade 1 and deemed clinically significant are usually concomitant disease or a manifestation of one and must be recorded accordingly. However, in some instances, they may be assessed as AEs (and therefore must be handled according to the directions in section 8.2) or as manifestations of already reported AEs. This decision will require a careful assessment of the abnormal result within the clinical context on a case-by-case basis and will depend on the Investigator's medical judgment.

Abnormal laboratory test results detected after the Screening Visit whose CTCAE grades are 2 or higher or still are CTCAE grade 1 and deemed clinically significant must be either recorded as AEs (and handled according to the directions in section 8.2) or linked to a concomitant disease or still to an already reported AE.

The principles for assessing and reporting abnormal laboratory test results, emerging after the Screening Visit, using CTCAE 4.03 grading scales are set up in Table 6:

Table 6 Principles for assessing and reporting abnormal laboratory test results

Grading	Clinically significant?	Is it a grade increase from previous results in study?§	Report?
Grade 1	No	Not applicable	No
Grade 1	Yes	No	No*
Grade 1	Yes	Yes	Yes, as AE or linked to an already reported AE
Grade 2 or higher	No/Yes	No	No*
Grade 2 or higher	No/Yes	Yes	Yes, as AE or linked to an already reported AE

Confidentiality Statement

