8.4.2 Reporting other abnormal findings

The other abnormal findings discovered during different clinical assessments (e.g., ECG, spirometry, physical examination, vital signs, body weight) should be evaluated for the clinical significance by the Investigator/designee based on his/her medical judgement. All abnormal clinical significant test results or clinical examination findings can, at the discretion of the Investigator, be reported as AEs and handled according to the directions from section 8.2.

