#### **Confidentiality Statement**

0.0001 will be displayed as 0. The geometric coefficient of variation (CV) will be reported as % with two decimal digits.

- For categorical data, frequency counts and percentages will be presented, missing values will be regarded as an own category if any missing value exists. Percentages will be presented to one decimal place. Percentages will not be presented for zero counts.

All analyses and summaries will be performed by product and overall, and separately for fixed and *ad libitum* use regimen when applicable.

Unless otherwise specified, summaries will be presented at Baseline and at each post baseline timepoint, including the change from baseline (calculated as difference from baseline).

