#### **Confidentiality Statement**

Vital signs values, changes from baseline (i.e. Day -1 or pre-fixed puffing measurement) and normality evaluation will be listed (Listing 15.3.6.8).

Descriptive statistics will be presented for values and changes from baseline and the number and percentage of subjects with normal/abnormal not clinically significant/abnormal clinically significant results will be reported by P3P variant and time point (Tables 15.2.6.16.1, 15.2.6.16.2, 15.2.6.16.3 and 15.2.6.16.4).

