#### **12.6.5.4 Spirometry**

Spirometry parameters (FEV1, FEV1 % predicted, FVC, FVC % predicted, FEV1/FVC) will be measured at Screening and Day 5 or early termination. Every measurement of spirometry parameters has to be assessed as normal or abnormal and, if abnormal, as clinically significant or not clinically significant. A diagnosis has to be provided in the CRF for all measurement of spirometry parameters assessed as abnormal and clinically significant.

Spirometry predicted values will be standardized to the National Health and Nutrition Examination Survey III predicted set (Hu and Cassano, 2000).

Spirometry parameters, changes from baseline (i.e. screening) and normality evaluation will be listed (Listing 15.3.6.9).

Descriptive statistics will be presented for values and changes from baseline and the number and percentage of subjects with normal/abnormal not clinically significant/abnormal clinically significant results will be reported by time point (Tables 15.2.6.17.1 and 15.2.6.17.2).

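### An off-schedule, clinically significant ECG, vital-sign or spirometry result that is not recorded as an AE is counted in no safety table

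*SAP*

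**What the plan says.** SAP 12.1.6 (Handling of Unplanned Data) reads: "Unscheduled post-product use assessments will be excluded from the summary statistics and only included in listings". It adds that such values are labelled as unscheduled in the listings and mapped to a study day that ends at midnight.

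SAP 12.1.3 sets the general layout: unless otherwise specified, "summaries will be presented at Baseline and at each post baseline timepoint". The vital-signs section applies this to the clinical classification: counts of normal, abnormal not clinically significant and "abnormal clinically significant results will be reported by P3P variant and time point". The ECG section uses the same layout. Spirometry "will be measured at Screening and Day 5 or early termination", and its counts are given by time point only.

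On the route to an AE, Protocol 8.4.2 says findings from other assessments ("e.g., ECG, spirometry, physical examination, vital signs, body weight) should be evaluated for the clinical significance by the Investigator/designee"), and then: "All abnormal clinical significant test results or clinical examination findings can, at the discretion of the Investigator, be reported as AEs". Laboratory results are treated differently. Under Protocol 8.4.1, post-Screening results of CTCAE grade 2 or higher, or grade 1 judged clinically significant, "must be either recorded as AEs (and handled according to the directions in section 8.2) or linked to a concomitant disease" or to an AE already reported.

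**The concern.** Leaving unscheduled values out of means at nominal times is normal practice. The SAP rule goes further: a value that appears only in listings is also absent from the counts of clinically significant results, which have no need of a nominal time. Extra ECGs, blood pressures or spirometry may be done because something looked wrong, so what is left out is not a random sample of the measurements.

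The AE tables would be the natural backstop, but for these three measures the step from a significant finding to an AE is optional. P3P is an inhaled powder for which the protocol (2.1.2) reports no human nicotine-absorption data. A reader of the safety tables should be able to rely on them for how many subjects had a clinically significant result after use.

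**Working it through.** No formula in the plan applies. The check is to follow one measurement through the reporting rules.

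Take a subject who, some time after using a variant, has an extra ECG that the Investigator classes as abnormal clinically significant. Suppose that it meets no seriousness criterion and is not entered as an AE.

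1. **Descriptive statistics (Table 15.2.6.18.2).** Excluded by SAP 12.1.6. This is reasonable.
2. **Interpretation counts (Table 15.2.6.18.1).** These are by variant and time point. The value belongs to no scheduled time point, and SAP 12.1.6 confines it to listings.
3. **Shift tables.** Protocol 12.6.3 planned one for ECG, but the SAP's list of changes from the protocol drops it. The SAP plans shift tables for laboratory data only.
4. **Worst-value or any-time tables.** Neither SAP 12.6.5 nor Table 21 has one for ECG, vital signs or spirometry.
5. **AE tables (15.2.6.1 onward).** Reached only if the Investigator chooses to record the finding (Protocol 8.4.2). The SAP asks for a diagnosis in the CRF for a clinically significant ECG, not for an AE entry. The AE definition in Protocol 8.1.1 does not settle it either: "medical judgment is required to establish whether a clinical finding (including an abnormal laboratory result) is a true AE".
6. **Listing 15.3.6.10.** The value appears here, labelled unscheduled.

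The path is the same for vital signs (Tables 15.2.6.16.1 to 15.2.6.16.4, Listing 15.3.6.8) and spirometry (Tables 15.2.6.17.1 and 15.2.6.17.2, Listing 15.3.6.9).

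The same trace ends differently in four cases:

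- **Laboratory result.** Protocol 8.4.1 requires recording or linkage and does not limit this to scheduled samples.
- **Serious event.** Protocol 8.3 makes reporting mandatory, so it reaches the AE tables.
- **Symptom that prompted the test.** Protocol 8.2.1 collects AEs at interview, so the symptom can be tabulated even though the measurement is not.
- **Spirometry at early termination.** This is a planned procedure (Protocol 9.6) and falls under a tabulated SAP time point.

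Scale: 6 sequences × 3 subjects = 18 randomized, and 1/18 = 5.6%. The safety population also includes exposed subjects who are never randomized, so the P3P 3 column may exceed 18 and one subject would then be less than 5.6% of it. Neither document gives a rate of unscheduled testing.

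**The case against.** The strongest reply is that little can slip through. Vital signs and ECG are scheduled after both regimens on each of Days 1 to 4, so an abnormality that persists is counted. An unscheduled test may simply be a recheck of a scheduled value already in the table. A subject who feels unwell has a symptom to report at interview, and AEs are the primary safety assessment. With 18 randomized subjects, the listings can be read line by line.

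Most of this stands, and it sets the size of the point. It does not remove it: a transient, non-serious finding that the Investigator does not record still has no table. The symptom backstop is also incomplete, because Protocol 7.8 says symptoms documented on questionnaires need not be recorded as AEs.

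Three stronger readings are tempting but not supported:

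- A reader might infer that laboratory abnormalities are hidden too. Unscheduled laboratory values do stay out of the laboratory counts and shift tables, but the mandatory rule in Protocol 8.4.1 largely secures their place among the AEs.
- A reader might infer that all lung-function data from Days 1 to 4 fall outside the tables and that spirometry counts by variant are biased. No spirometry is scheduled or triggered on those days in a subject who continues, spirometry after a discontinuation is tabulated, and spirometry is not tabulated by variant.
- A reader might infer a demonstrated downward bias in the subjects with problems. That depends on unscheduled tests occurring, showing something new, and not being recorded as AEs. The documents give no frequency for any of these.

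**Conclusion.** The point holds in a narrow form. By its stated rules, the plan counts in no safety table a clinically significant ECG, vital-sign or spirometry result that is non-serious, off-schedule and not recorded as an AE. The value is not lost, since it stays in the listings. This is a gap in the completeness of the tables and does not invalidate the safety analysis. One such subject would change a column of 18 from 0% to 5.6%; how often this would happen cannot be estimated from the documents.

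The conclusion assumes that SAP 12.1.6 means what it says, so that listings-only excludes category counts as well as means. It is a cheap improvement.

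**What to change.** Keep unscheduled values out of the descriptive statistics and counts at nominal time points. Add to SAP 12.1.6, and to the interpretation tables for vital signs (15.2.6.16.2), spirometry (15.2.6.17.1) and ECG (15.2.6.18.1), a row giving the number and percentage of subjects with any post-use result assessed as abnormal clinically significant, scheduled or unscheduled, by the exposure periods of SAP 12.6.5.1. Show the scheduled-only count alongside.

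Three practical notes:

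- Count by exposure period, not by the midnight-bounded study day of SAP 12.1.6. The two differ for a measurement after midnight and before the next morning's use.
- Scheduled Day 5 spirometry will fall in the period of the last variant used, although a completer has by then used all four. A footnote should say so.
- Count any clinically significant result, not a worst value. Worst is undefined for measures that can be abnormal in either direction.

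The cost is one SAP paragraph and a little programming. The SAP already requires every measurement of these three types to be classified, so no new data are needed. The drawback is that an any-time count rises with how often a subject is retested; the scheduled-only count beside it makes that visible.

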### **12.1.7 Significance Level for Inferential Analysis**

This study has no formal pre-specified hypotheses associated with the study objectives. Unless stated otherwise, all quoted confidence intervals are two-sided 95% confidence intervals (CI)

### **12.1.8 Multiple Comparisons/Multiplicity**

No formal adjustment of the test-wise alpha level for multiple testing is necessary, as this study is descriptive in nature and no claim will be made based on the outcome of the individual CI values.

## **12.2 Disposition of Subjects**

The number and percent of subjects will be summarized for the following categories (Table 15.2.1.1):

- screen failures (including reasons for screen failure);

#### **Confidentiality Statement**

Data and information contained in this document are considered to constitute trade secrets and confidential commercial information, and the legal protections provided to such trade secrets and confidential information are hereby claimed under the provisions of applicable law. No part of this document may be publicly disclosed without the written consent of Philip Morris Products S.A.

- enrolled subjects;
  - enrolled subjects exposed;
  - enrolled subjects who discontinued before randomization and exposed (including reasons for not randomizing)
  - enrolled subjects who discontinued before randomization and not exposed (including reasons for not randomizing);
  - enrolled subjects who completed the safety follow-up;
- randomized subjects;
  - randomized subjects who completed;
  - randomized subjects who discontinued (including reasons for discontinuation);
  - randomized subjects who completed the safety follow-up.

The number and percent of subjects included into the analysis populations will be summarized as follows (Table 15.2.1.1.1):

- screened population;
- enrolled population;
- safety population;
- randomized population;
- PK population;
- randomized subjects excluded from PK population;
  - reasons for exclusion from the PK population.

Unmet inclusion and exclusion criteria will be listed for each screened subjects having any unmet criterion (Listings 15.3.1.1).

Supportive listings on subjects' disposition will be provided (Listings 15.3.1.1, 15.3.1.2.1, 15.3.1.2.2, 15.3.1.3). A listing of randomization schemes and codes will also be provided (Listing 16.1.7).

The number and percent of subjects with protocol deviations, and the number of protocol deviations, will be summarized (Listing 15.3.1.4; Table 15.2.1.2). Summaries will be broken down by main deviation category (major/minor), sub-categories, and evaluability impact. Subjects will be counted once per deviation category, and can be counted for more than one deviation category.

## **12.3 Demographics and Other Baseline Characteristics**

Demographic and baseline characteristics will be summarized for the PK population, and listed for all screened subjects. This summary will also be performed for the safety population.

Summaries will include sex, age, race, height, weight and BMI, smoking history, FTND and cytochrome P450 2A6 (CYP2A6) activity. Demographics will be presented by sex as specified in Section 12.1.1 "Stratified Presentation".

### **Confidentiality Statement**

No inferential analyses will be presented for the demographic and baseline characteristics.

### **12.3.1 Demographics**

Sex, age, race, height, weight and BMI will be listed and summarized as specified in Section 12.3 "Demographics and Other Baseline Characteristics" (Listing 15.3.1.5, Tables 15.2.1.3.1, 15.2.1.3.1.1 and 15.2.1.3.2)

### **12.3.2 Smoking History and Habits**

The following smoking characteristics at Screening will be listed and summarized as specified in Section 12.3 "Demographics and Other Baseline Characteristics" (Listing 15.3.1.6, Tables 15.2.1.3.1, 15.2.1.3.1.1 and 15.2.1.3.2):

- Smokers for at least the past 3 consecutive years
- Number of years the subjects have smoked
- Average cigarettes per day since smoking start
- Average cigarettes per day over the past four weeks
- Average menthol cigarettes per day over the past four weeks
- Brand of cigarettes (listed only)

### **12.3.3 FTND Questionnaire at Screening**

FTND score value and the number and percentage of subjects in each category (mild/moderate/severe) will be presented. Data will be listed and summarized as reported in Section 12.3 "Demographics and Other Baseline Characteristics" (Listing 15.3.1.7, Tables 15.2.1.3.1, 15.2.1.3.1.1 and 15.2.1.3.2).

### **12.3.4 CYP2A6 Activity at Admission**

CYP2A6 activity will be calculated as the metabolic ratio of trans 3' hydroxycotinine and cotinine measured at Admission (Day -1), as described in Section 7.2.1 "CYP2A6". Data will be listed and summarized as reported in section 12.3 "Demographics and Other Baseline Characteristics" (Listing 15.3.1.8, Tables 15.2.1.5.1, 15.2.1.5.1.1 and 15.2.1.5.2).

### **12.3.5 Medical History and Concomitant Diseases**

Medical history is defined as any condition that started and ended prior to the ICF signature at Screening. Medical history will be coded using Medical Dictionary for Regulatory Activities (MedDRA) version 20.1, listed and summarized by System Organ Class (SOC) and Preferred Term (PT) within SOC. The number and percent of subjects with medical history diseases, and the number of medical history diseases, will be summarized (Listing 15.3.1.9, Table 15.2.1.3.3).

#### **Confidentiality Statement**

Data and information contained in this document are considered to constitute trade secrets and confidential commercial information, and the legal protections provided to such trade secrets and confidential information are hereby claimed under the provisions of applicable law. No part of this document may be publicly disclosed without the written consent of Philip Morris Products S.A.

Concomitant disease is defined as any condition diagnosed at Screening or was ongoing at Screening. Concomitant disease will be coded using MedDRA version 20.1, listed and summarized by SOC and PT within SOC. The number and percent of subjects with concomitant diseases, and the number of concomitant diseases, will be summarized (Listing 15.3.1.9, Table 15.2.1.3.4).

### **12.3.6 Other Data**

Other data collected at Screening and/or Admission will be listed by subject (Listing 15.3.1.10). These data are as follows:

- Serology for HIV and Hepatitis B and C (Screening)
- Urine cotinine test (Screening)
- Urine pregnancy test (Screening, Day -1, Day 5, Early Termination and Unscheduled assessments)
- Urine drug screen (Screening, Day -1)
- Alcohol breath test (Screening, Day -1 and Unscheduled assessments)

